### **3.5.2. Outliers**

Outliers will be identified during the data management and data analysis process, but no sensitivity analyses will be conducted. All data will be included in the data analysis.

### **3.6. Data Handling Conventions and Transformations**

By-subject listings will be presented for all subjects in the Safety Analysis Set and sorted by subject ID number, visit date, and time (if applicable) unless otherwise specified. Data collected on log forms, such as AEs, will be presented in chronological order within subject.

Age (in years) on the date of the first dose of study drug and sex at birth will be used for analyses and presentation in listings.

If a subject was not dosed with study drug at all, then the date the informed consent was signed will be used instead of the first dose date of study drug. For some countries, only birth year is collected on the eCRF. In those cases, “01 July” will be used for the unknown birth day and month for the purpose of age calculation, unless age is captured on the eCRF.

Non-PK data that are continuous in nature but are less than the LLOQ or above the upper LOQ will be imputed as follows:

- A value that is one unit less than the limit of quantitation will be used for calculation of descriptive statistics if the datum is reported in the form of “< x” (where x is considered the limit of quantitation). For example, if the values are reported as < 50 and < 5.0, values of 49 and 4.9, respectively, will be used for calculation of summary statistics. An exception for this rule is any value reported < 1. For the values reported as < 1 or < 0.1, value of 0.9 or 0.09 will be used for calculation of summary statistics.
- A value that is one unit above the limit of quantitation will be used for calculation of descriptive statistics if the datum is reported in the form of “> x” (where x is considered the limit of quantitation). Values with decimal points will follow the same logic as above.
- The limit of quantitation will be used for calculation of descriptive statistics if the datum is reported in the form of “≤ x” or “≥ x” (where x is considered the limit of quantitation).

The COBAS® AmpliPrep/COBAS® TaqMan® HCV Test, v2.0 for use with the High Pure System was used to determine HCV RNA results in this study. The LLOQ of the assay is 15 IU/mL.

When the calculated HCV RNA value is within the linear range of the assay, then the result will be reported as the “<< numeric value>> IU/mL”. This result will be referred to in this document as the numeric result or as “≥ LLOQ detected” for categorical result.

When HCV RNA is not detected, the result is reported as “No HCV RNA detected” or “target not detected”. This result will be referred to in this document as “< LLOQ target not detected” or “< LLOQ TND”.

When the HCV RNA IU/mL is less than LLOQ of the assay, the result is reported as “< 15 IU/mL HCV RNA detected”. This result will be referred to in this document as “< LLOQ detected”.

The overall category of HCV RNA < LLOQ includes “< LLOQ TND” and “< LLOQ detected.”

For numerical HCV RNA data, values below LLOQ will be set to the LLOQ 1 IU/mL (ie, 14 HCV RNA IU/mL). HCV RNA values returned as “No HCV RNA detected” will also be set to 14 IU/mL.

If methods based on the assumption that the data are normally distributed are not adequate, analyses may be performed on transformed data (eg, log10 scale) or nonparametric analysis methods may be used, as appropriate.

Natural logarithm transformation will be used for plasma/blood concentrations and analysis of PK parameters. Plasma concentration values that are below the lower limit of quantitation (BLQ) will be presented as “BLQ” in the concentration data listing. Values that are BLQ will be treated as 0 at predose time points, and one-half the value of the LLOQ at postdose time points for summary purposes.

For the presentation of summary and order statistics, if at least 1 subject has a concentration value of BLQ for the time point, then the minimum value will be displayed as “BLQ” If more than 25% of the subjects have a concentration data value of BLQ for a given time point, then the minimum and Q1 values will be displayed as “BLQ” If more than 50% of the subjects have a concentration data value of BLQ for a given time point, then the minimum, Q1, and median values will be displayed as “BLQ” If more than 75% of the subjects have a concentration data value of BLQ for a given time point, then the minimum, Q1, median, and Q3 values will be displayed as “BLQ” If all subjects have concentration data values of BLQ for a given time point, then all order statistics (minimum, Q1, median, Q3, and maximum) will be displayed as “BLQ”.

### **3.7. Visit Windows**

#### **3.7.1. Definition of Study Day**

Study day is the day relative to the date of the first dose of study drug. Study Day 1 will be defined as the day of first dose of study drug administration.

Study day will be calculated from the date of first dose of study drug administration and derived as follows:

- For postdose study days: Assessment Date - First Dose Date + 1
- For days prior to the first dose: Assessment Date - First Dose Date

The last dose date for the study drug will be the end date on study drug administration eCRF for the record where the “subject permanently discontinued” flag is ‘Yes’.

If there are subjects for whom the date of last study drug is unknown due to the reason that the subject was lost to follow-up and not able to be contacted, the date of last dose will be estimated using the maximum of nonmissing study drug start or stop dates, visit dates and laboratory collection dates (posttreatment visits and unscheduled visits are not included).

### 3.7.2. Analysis Windows

Subject visits might not occur on protocol-specified days. Therefore, for the purpose of analysis, observations will be assigned to analysis windows.

The baseline value will be the last nonmissing value on or prior to the first dose date of study drug.

HCV RNA, vital signs, and safety laboratory data collected up to the last dose date + 3 days are considered to be on-treatment data and HCV RNA, vital signs and safety laboratory data collected after the last dose date + 3 days are considered posttreatment data. The analysis windows for on-treatment HCV RNA, vital signs and safety laboratory data are provided in [Table 3-1](#).

**Table 3-1. Analysis Windows for On-treatment HCV RNA, Vital Signs and Safety Laboratory Data**

Nominal Visit	Nominal Day	Lower Limit	Upper Limit
Baseline	1	(none)	1
Week 1	7	2	18
Week 4	28	19	42
Week 8	56	43	70
Week 12	84	71	≥ 85

Subjects who participated in PK Lead-in Phase will immediately roll over into Treatment Phase with no interruption of study drug administration until the appropriateness of the dose is confirmed by PK and safety data from the PK-Lead-in. These subjects will start at the Week 4 visit of the Treatment Phase. Week 1 records for these subjects will be chosen from Day 7 in the PK Lead-in Phase.

HCV RNA, vital sign, and safety laboratory data collected after the last dose date + 3 days will be assigned to the posttreatment follow-up (FU) visits. Visit windows will be calculated from the last dose date (ie, FU Day = collection date minus the last dose date) as shown in [Table 3-2](#).

**Table 3-2. Analysis Windows for Posttreatment HCV RNA, Body Weight, Height, Vital Sign and Safety Laboratory Data**

Nominal FU a Visit	HCV RNA, Body weight and Height			Vital Signs and Safety Laboratory Data b		
	Nominal FU Day	Lower Limit	Upper Limit	Nominal FU Day	Lower Limit	Upper Limit
FU 4	28	21	69	28	4	30
FU 12	84	70	146	NA	NA	NA
FU 24	168	147	210	NA	NA	NA

a FU x visit posttreatment Week x follow up visit.

b Vital signs (blood pressure, pulse, respiratory rate, and temperature) and safety labs will only be summarized for the FU 4 visit (up to 30 days after last dose).

### 3.7.3. Selection of Data in the Event of Multiple Records in an Analysis Window

Depending on the statistical analysis method, single values may be required for each analysis window. For example, change from baseline by visit usually requires a single value, whereas a time-to-event analysis would not require 1 value per analysis window.

If multiple valid nonmissing numeric observations exist in an analysis window, records will be chosen based on the following rules if a single value is needed:

- For baseline, the last available record on or prior to the date of the first dose of study drug will be selected. If there are multiple records with the same time or no time recorded on the same day, average (arithmetic mean) will be used for the baseline value.
- For postbaseline visits:

The record closest to the nominal day for that visit will be selected except for HCV RNA posttreatment follow-up visits, for which the latest record in the analysis window will be selected.

If there are 2 records that are equidistant from the nominal day, the later record will be selected.

If there is more than 1 record on the selected day, the average will be taken, unless otherwise specified.

If multiple valid nonmissing categorical observations exist in a window, records will be selected as follows:

- For baseline, the last available record on or prior to the date of the first dose of study drug will be selected. If there are multiple records with the same time or no time recorded on the same day, the value with the lowest severity will be selected (eg, normal will be selected over abnormal).
- For postbaseline visits, follow the same rules described above for postbaseline numeric observations, except that if there are multiple records on the same day, the most conservative value will be selected (eg, abnormal will be selected over normal).

## 4. SUBJECT DISPOSITION

### 4.1. Subject Enrollment and Disposition

A summary of subject enrollment will be provided by age group for each country, investigator within a country, and overall. The summary will present the number and percentage of subjects in the Safety Analysis Set. For each column, the denominator for the percentage calculation will be the total number of subjects analyzed for that column.

A summary of subject disposition will be provided by HCV genotype (1 [further broken down to 1a and 1b], 2, 3, 4, 5, 6, or other, as appropriate, and total) for each age group. This summary will present the number of subjects screened, enrolled, enrolled but never treated, and the number and percentage of subjects in each of the categories listed below. For the “Treated” category, the denominator for the percentage calculation will be the total number of subjects enrolled. For all other categories, the denominator for the percentage calculation will be the total number of subjects in the Safety Analysis Set.

- Treated (Safety Analysis Set)
- In FAS
- In Lead-in Phase PK Analysis Set
- In Population PK Analysis Set
- Completed study treatment
- Did not complete study treatment with reasons for premature discontinuation of study treatment
- Completed the study
- Did not complete the study with reason for premature discontinuation of study

Among subjects who completed the study treatment and who discontinued study treatment, the following number and percentage of subjects will be summarized:

- Subjects who had no HCV posttreatment Week 4 assessment and thereafter (No HCV FU-4 and thereafter)
- Subjects who had HCV posttreatment Week 4 assessment but no HCV posttreatment Week 12 assessment and thereafter (With HCV FU-4 but no FU-12 and thereafter)

If a subject did not have any HCV RNA assessment  $\geq 21$  days after the last dose of any study drug (ie, lower bound of FU-4 visit for HCV RNA data), the subject is categorized as having “No HCV FU-4 and thereafter”. If a subject had the HCV FU-4 assessment but did not have any HCV RNA assessment  $\geq 70$  days after the last dose of any study drug (ie, lower bound of FU-12 visit for HCV RNA data), the subject is categorized as having “With HCV FU-4 but No FU-12 and thereafter”.

In addition, the total number of subjects who were enrolled, and the number of subjects in each of the disposition categories listed above will be displayed in a flowchart.

The following by-subject listings will be provided by subject ID number in ascending order to support the above summary tables:

- Disposition of subjects who complete study treatment and study
- Disposition of subjects who did not complete study treatment and/or study with reasons for premature discontinuation of study drug and/or study
- Lot number and kit ID (if applicable)

#### **4.2. Extent of Exposure**

Extent of exposure to study drug will be examined by assessing the total durations of study drug exposure and the level of adherence to the study drug regimen specified in the protocol.

##### **4.2.1. Durations of Exposure to Study Regimen**

Total duration of exposure to study drug will be defined as last dose date minus first dose date plus 1, regardless of any temporary interruptions in study drug administration, and will be expressed in weeks using up to 1 decimal place (eg, 4.5 weeks).

The total durations of exposure to study drug will be summarized for each age group using descriptive statistics (n, mean, SD, median, Q1, Q3, minimum, and maximum) and using the number (ie, cumulative counts) and percentage of subjects exposed through the following time periods: Baseline (Day 1), Week 1 (Day 7), Week 4 (Day 28), Week 8 (Day 56), and Week 12 (Day 84). A 3-day window is applied to the last planned on-treatment visit to match with the protocol-specified visit window. Summaries will be provided for the Safety Analysis Set.

##### **4.2.2. Adherence to Study Drug**

The level of adherence to the study drug regimen will be assessed based on the total amount of study drug administered relative to the total amount of study drug prescribed.

Given the fact that multiple formulations of the study drug have been used in this study, the adherence will be calculated based on the amount of SOF/VEL (mg) by the following formula:

$$\text{Level of Adherence(\%)} = \left( \frac{\text{Total Amount of Study Drug Administered}}{\text{Total Amount of Study Drug Prescribed at baseline}} \right) \times 100$$

Where the presumed total amount of study drug (mg) administered to a subject will be determined by the data collected on the drug accountability eCRF using the following formula:

$$\text{Total Amount of Study Drug (mg) Administered} = \left( \sum \text{Total Amount of Study Drug (mg) Dispensed} \right) - \left( \sum \text{Total Amount of Study Drug (mg) Returned} \right)$$

Note: If calculated adherence is greater than 100%, the result will be set to 100%.

The total amount of prescribed SOF/VEL (mg) for 12 weeks are as follows:

Age Group and Body Weight	SOF/VEL Daily Dose	Total Amount of SOF/VEL Prescribed for 12 Weeks
12 to <18 years any weight	500 mg/day	42000 mg
6 to <12 years any weight	250 mg/day	21000 mg
3 to <6 years weighing ≥17 kg	250 mg/day	21000 mg
3 to < 6 years weighing <17 kg	187.5 mg/day	15750 mg

Subjects who prematurely discontinue study drug for lack of efficacy (ie, virologic failure) will have the total amount of study drug prescribed calculated up to the first date when virologic failure criteria were met. For virologic failure confirmed by 2 consecutive measurements the date of the first measurement will be used. If there are study drug bottles dispensed on or after the subject first met virologic failure criteria, these bottles will not be included in the calculation of adherence. If a bottle is dispensed and the bottle is returned empty, then the number of tablets returned will be entered as zero. If a bottle is dispensed but not returned (missing), the number of tablets taken from that bottle will be counted as zero.

Descriptive statistics for the level of adherence (n, mean, SD, median, Q1, Q3, minimum, and maximum) with the number and percentage of subjects belonging to adherence categories (e.g. < 80%, ≥ 80 to < 90%, ≥ 90%) will be provided by age group for the Safety Analysis Set. No inferential statistics will be provided for duration of exposure and adherence to study drug.

A separate by-subject listing of study drug administration and drug accountability will be provided by subject ID number (in ascending order) and visit (in chronological order).

#### 4.3. Protocol Deviations

A summary of important protocol deviations will be provided by the Clinical Operations group for subjects in the Safety Analysis Set.

Subjects who received study drug other than their enrolled treatment assignment will be listed with the start and stop dates that they received incorrect study treatment.

## 5. BASELINE CHARACTERISTICS

### 5.1. Demographics

Subject demographic variables (ie, age, sex, race, and ethnicity) will be summarized by HCV genotype (1 [further broken down to 1a and 1b], 2, 3, 4, 5, 6, or other, as appropriate, and total) in each age group using descriptive statistics (n, mean, SD, median, Q1, Q3, minimum, and maximum) for age, and using the numbers and percentages of subjects for sex, race, and ethnicity. Age is calculated in years at the date of initial study drug administration. If a subject did not receive study drug after enrollment, the subject's age will be calculated from the date that the subject signed the informed consent form. The summary of demographic data will be provided for the Safety Analysis Set.

A by-subject demographic listing will be provided by subject ID number in ascending order.

### 5.2. Other Baseline Characteristics

Other baseline characteristics include:

- weight in kg
- height in cm
- body mass index (BMI; in kg/m^2)
- HCV genotype (1 [further broken down to 1a and 1b], 2, 3, 4, 5, 6, or other, as appropriate)
- cirrhosis (presence, absence, not determined)
- IL28B (CC, CT, TT)
- baseline HCV RNA (IU/mL) (< 800,000 IU/mL, ≥ 800,000 IU/mL)
- baseline HCV RNA (log10 IU/mL) as a continuous variable and as categories (< 6 log10 IU/mL, ≥ 6 log10 IU/mL)
- baseline ALT (U/L) as a continuous variable and as categories (≤1.5 × ULN, > 1.5 × ULN)
- estimated glomerular filtration rate (eGFR) using Schwartz Formula (mL/min/1.73m^2)
- prior treatment experience (treatment naïve, treatment experienced)
- most recent response to prior HCV treatment (non-response, relapse/breakthrough, unknown) for treatment experienced subjects

- mode of HCV Infection
- bone age in years
- Tanner Stage

Estimated glomerular filtration rate will be calculated using Schwartz Formula ( $\text{mL}/\text{min}/1.73\text{m}^2$ )  $k \times L/\text{Scr}$  [(k is a proportionality constant, for adolescent females  $\geq 12$  years old is 0.55; for adolescent males  $\geq 12$  years old is 0.70, and for children 3- <12 years old is 0.55); L is height in centimeters (cm); and Scr is serum creatinine (mg/dL)].

These baseline characteristics will be summarized by HCV genotype (1 [further broken down to 1a and 1b], 2, 3, 4, 5, 6, or other, as appropriate, and total) in each age group using descriptive statistics (n, mean, SD, median, Q1, Q3, minimum, and maximum) for continuous variables and using the numbers and percentages of subjects for categorical variables. The summary of baseline characteristics will be provided for the Safety Analysis Set.

A by-subject listing of other baseline characteristics will be provided by subject ID number in ascending order.

### **5.3. Medical History**

General medical history (ie, conditions not specific to the disease being studied) data will be collected at screening and listed only. General medical history data will not be coded. A by-subject listing of disease-specific medical history will be provided by subject ID number (in ascending order) and medical history of abnormalities (in chronological order).

## 6. EFFICACY ANALYSES

### 6.1. Key Efficacy Endpoint

#### 6.1.1. Definition of the Key Efficacy Endpoint

The key efficacy endpoint is SVR12 defined as HCV RNA < LLOQ (ie, < 15 IU/mL) 12 weeks after discontinuation of the study drug in the FAS. The COBAS® AmpliPrep/COBAS® TaqMan® HCV Test, v2.0 for use with the High Pure System will be used to measure HCV RNA.

#### 6.1.2. Analysis Methods for the Key Efficacy Endpoint

No inferential statistics will be provided for efficacy endpoints. No statistical comparison will be conducted.

The point estimates of SVR12 rate and 2-sided 95% exact CI based on Clopper-Pearson method {Clopper 1934} will be provided by age group for the FAS.

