- To evaluate the emergence of viral resistance to SOF and VEL during treatment and after cessation of treatment
- To evaluate the effect of treatment with SOF/VEL FDC on quality of life as measured by PedsQL™ Pediatric Quality of Life survey
- To evaluate the effect of SOF/VEL FDC on growth and development of pediatric subjects during and after treatment
- To evaluate the acceptability, including palatability, of formulations used in the study

The exploratory objective of this study is:

Study Design:

Open-label, multi-cohort, two-part study evaluating the PK, safety, and antiviral activity of SOF/VEL FDC in pediatric subjects with chronic HCV infection.

Pediatric subjects with chronic HCV infection of any HCV genotype, including indeterminate or mixed genotypes, will be enrolled. Both treatment-naïve and treatment-experienced subjects will be eligible, with at least 20 and up to 40 subjects overall allowed to be treatment-experienced.

PK Lead-in Phase: The PK Lead-in Phase will evaluate and/or confirm age appropriate SOF/VEL FDC doses by analyzing PK, safety, and antiviral activity of SOF/VEL FDC through 7 days of dosing with intensive PK sample collection at steady state on Day 7. Three sequential age-based cohorts of at least 17 subjects each will be enrolled:

- Cohort 1: 12 to < 18 years old
- Cohort 2: 6 to < 12 years old
- Cohort 3: 3 to < 6 years old
 - At least 6 subjects weighing \geq 17 kg
 - At least 6 subjects weighing < 17 kg

PK Lead-in subjects in each cohort will immediately roll over into the Treatment Phase as they complete Day 7 of the PK Lead-in Phase. They will continue dosing with the same dose of SOF/VEL FDC with no interruption of study drug administration and will follow the Treatment Phase visit schedule for all subsequent visits.

The PK and safety data through Day 7 of each cohort will be reviewed to confirm the appropriateness of the SOF/VEL FDC dose for the Treatment Phase in that age group as well as to determine the dose to be evaluated in the PK Lead-in Phase of the next age cohort.

Treatment Phase: The Treatment Phase will be initiated sequentially by age group after confirmation of the age-appropriate SOF/VEL FDC dose as follows (including subjects that participated within the PK Lead-in Phase):

- Group 1: Approximately 100 subjects aged 12 to < 18 years
— Includes subjects enrolled in Cohort 1
- Group 2: Approximately 100 subjects aged 3 to < 12 years
— Includes subjects enrolled in Cohorts 2 and 3

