Criteria for Evaluation:

- Safety:** AEs, laboratory tests, physical examinations, and vital sign measurements will be collected throughout the study.
- Efficacy:** Efficacy will be evaluated using scheduled assessments of HCV RNA performed using COBAS[®] AmpliPrep/COBAS[®] TaqMan[®] HCV test.
- Pharmacokinetics:** For subjects in the PK Lead-in, the steady-state PK of VEL, SOF, and its major metabolite (GS-331007) will be assessed at Day 7. Plasma PK parameters such as C_{max} , T_{max} , C_{last} , T_{last} , C_{tau} , AUC_{tau} , CL/F , Vz/F and $t_{1/2}$ will be estimated, as appropriate.
- Intensive PK and safety results from the PK Lead-in Phase of each cohort will be reviewed to confirm the appropriateness of the evaluated SOF/VEL FDC dose for the Treatment Phase in that age group.
- For all subjects in the Treatment Phase, sparse PK blood samples will be collected at all visits while on treatment. The PK of SOF, its primary metabolite GS-331007, and VEL will be assessed.

Statistical Methods: For the PK Lead-in, the primary plasma PK parameters are AUC_{tau} , for SOF, GS-331007, and VEL. All PK parameters will be summarized by cohort. The effect of age and SOF/VEL FDC dose on PK will be explored.

For the Treatment Phase, the primary safety endpoint is review of any AEs with a focus on AEs that lead to discontinuation of study drug. The key efficacy endpoint is SVR12 in all enrolled and treated subjects. The point estimate of the SVR12 rate and the 2-sided 95% exact confidence interval based on the Clopper-Pearson method will be provided. The secondary efficacy endpoints include SVR4 and SVR24.

Clinically relevant subgroup analyses on SVR12 may be conducted as appropriate (ie, assuming that adequate numbers of patients in these subsets are available for analysis).

All continuous endpoints will be summarized using an 8-number summary (n, mean, standard deviation, median, Q1, Q3, minimum, and maximum). All categorical endpoints will be summarized by number and percentage of subjects who meet the endpoint definition.

Safety endpoints will be analyzed by the number and percent of subjects with events or abnormalities for categorical values or by the 8-number summary (n, mean, standard deviation, median, Q1, Q3, minimum, maximum) for continuous data.

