8.4. Efficacy Analysis

8.4.1. Analysis of the Key Efficacy Endpoint

The key efficacy endpoint is SVR12 on the FAS. The analysis of SVR12 will be performed after all enrolled subjects have been followed through posttreatment Week 12 or discontinued from the study. The point estimate of the SVR12 rate and the 2-sided 95% exact CIs based on Clopper-Pearson method will be calculated.

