8.8. Sample Size

With approximately 100 subjects enrolled into the 12 to < 18 years of age group and approximately 100 subjects enrolled into the 3 to < 12 years of age group, a 2-sided 95% exact confidence interval of the SVR12 rate in each age group will extend at most 20%.

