### **1.3. Sample Size and Power**

With approximately 100 subjects enrolled into the 12 to < 18 years of age group and approximately 100 subjects enrolled into the 3 to < 12 years of age group, a 2-sided 95% exact confidence interval of the SVR12 rate in each age group will extend at most 20%.

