### 6.4. Changes From Protocol-Specified Efficacy Analyses

There are no changes from protocol-specified efficacy analyses.

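### Does giving SVR12 by age group in SAP 6.1.2 drop the all-treated rate and the 3 to <12 rate that the protocol sets up?

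*SAP*

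**What the plan says.** **Protocol.** The synopsis states: "The key efficacy endpoint is SVR12 in all enrolled and treated subjects". Section 8.4.1 puts it as "The key efficacy endpoint is SVR12 on the FAS". Both attach a point estimate and a Clopper-Pearson 95% interval, and neither mentions an age split. Section 8.8 rests the sample size on two groups, about 100 adolescents and "approximately 100 subjects enrolled into the 3 to < 12 years of age group", and states the precision of the rate in each. Section 8.4.2 leaves the details of the efficacy analyses to the SAP.

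**SAP.** Section 6.1.1 keeps the full analysis set (FAS) as the population for SVR12. Section 6.1.2 says the estimate and interval "will be provided by age group for the FAS". Section 6.4 adds: "There are no changes from protocol-specified efficacy analyses".

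**What an age group is.** The Protocol synopsis says "The Treatment Phase will be initiated sequentially by age group after confirmation of the age-appropriate SOF/VEL FDC dose as follows" and then lists two groups, the second being "Group 2: Approximately 100 subjects aged 3 to < 12 years". Protocol 3.3.2 uses similar words for three bands: 12 to <18, 6 to <12 and 3 to <6. SAP 1.2 gives two enrolment groups and then three groups for the order of enrolment. SAP 1.2.2 and the adherence table in SAP 4.2.2 use the three bands. SAP 1.3 uses two. SAP 3.2, which deals with grouping, does not define the term.

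**The concern.** On a first reading, two estimates seem to be lost between protocol and SAP.

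1. **The all-treated rate.** The protocol names it as the key efficacy endpoint, but SAP 6.1.2 has no all-age row however age group is read. SAP 3.2 does not help, because for the primary analysis it points back to section 6.1. The total in SAP 6.1.3 is taken over genotypes within an age group, not over ages.
2. **The 3 to <12 rate.** Under the three-band reading, SAP 6.1.2 gives 6 to <12 and 3 to <6 separately and not the combined group for which precision was stated.

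If both were lost, the SAP's statement of no changes would be wrong. The rates actually planned for younger children would carry no stated precision, since no section fixes how the 100 or so children divide beyond the minimum of 17 per PK cohort. It would also be unclear which SVR12 figure is the main efficacy result. That would matter if the choice among rates could be made after seeing the data to flatter the result, or if the missing rates could not be recovered.

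**Working it through.** **Inputs.** About 100 aged 12 to <18 and about 100 aged 3 to <12 (Protocol 8.8, SAP 1.3); about 200 in total (Protocol 4.1); at least 17 per PK cohort (SAP 1.2.1). The split of the younger group and the SVR12 values below are assumptions.

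**Formula.** For x responders out of n, the Clopper-Pearson 95% limits are the 0.025 quantile of Beta(x, n − x + 1) and the 0.975 quantile of Beta(x + 1, n − x). The width is the upper limit minus the lower.

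**Step 1: the plan's own figure.** SAP 1.3 says "a 2-sided 95% exact confidence interval of the SVR12 rate in each age group will extend at most 20" percent. At n = 100 the widest interval is at x = 50: 39.83% to 60.17%, a width of 60.17 − 39.83 = 20.34 points. That rounds to 20, so the statement refers to full width with about 100 per group. A width of 20.0 or less in every case needs n = 104 (19.93), which is consistent with approximately 100.

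**Step 2: what the three bands would do.** With at least 17 in each younger band, 3 to <6 can hold 17 to 83 of 100, and the smaller band has at most 50.

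| n | Worst-case width (points) | Mean width if true SVR12 is 90% | 95% | 99% |
|---|---|---|---|---|
| 17 | 49.2 | 31.8 | 26.4 | 21.0 |
| 50 | 28.9 | 18.0 | 13.8 | 8.8 |
| 100 | 20.3 | 12.6 | 9.4 | 5.2 |
| 200 | 14.3 | 8.7 | 6.5 | 3.3 |

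The worst case sits near 50% response, far from the 97.3% and 99.0% that Protocol 1.2.2.2 reports for 12 weeks of SOF/VEL in two earlier studies. At an assumed 95%, the mean width stays within 20 points once a band has 27 or more children. The table describes how precise a small band is. It does not measure the effect of leaving out a pooled row, and adding such a row would not narrow any band.

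**Step 3: can the unlisted rates be recovered?** Suppose 16/17 in one younger band (94.1%, 71.3% to 99.9%), 79/83 in the other (95.2%, 88.1% to 98.7%) and 95/100 adolescents.

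- 3 to <12: (16 + 79)/(17 + 83) = 95/100 = 95.0%, interval 88.7% to 98.4%.
- All treated: (95 + 95)/(100 + 100) = 190/200 = 95.0%, interval 91.0% to 97.6%.

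The bands do not overlap and share one endpoint definition and one imputation rule. The sums are therefore exactly the pooled counts, and the interval method is already specified.

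**Step 4: is either rate really absent?**

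- *All ages.* SAP 6.2.2 plans a table of HCV RNA below LLOQ at each posttreatment visit, by genotype and total, with exact intervals. SVR12 is HCV RNA below LLOQ 12 weeks after treatment (SAP 6.1.1). The SVR12 outcome table earlier in that section is explicitly for each age group; this one states no age split. Read literally, its Week 12 total is the all-age rate.
- *3 to <12.* SAP 1.3 is the one place in the SAP that joins the SVR12 rate to each age group, and there 3 to <12 is itself an age group. On that reading SAP 6.1.2 does report it. The three-band uses concern enrolment order (SAP 1.2, 1.2.2) and dose (SAP 4.2.2).

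**The case for a change.** The strongest case for a change is that it is cheap and that the gap is real. On any reading, SAP 6.1.2 lists no all-age row, while the protocol's endpoint covers all treated subjects. The 6.2.2 table is a secondary output, SAP 3.2 says efficacy is generally by age group, and the word overall in that table could mean observed plus imputed. In a trial with no hypothesis test, the estimate and its interval are the efficacy result, so it is fair to ask that the main one be named in advance. A few sentences and two table columns would do it, with no new data.

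Part of this stands. The all-age row is not listed in 6.1.2, age group is not defined, and 6.2.2 supports an all-age rate without guaranteeing it.

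The charge of contradiction does not stand. The protocol sentences can be read as fixing the analysis population, which SAP 6.1.1 and 6.1.2 both keep. Protocol 8.8 already speaks of an SVR12 rate in each age group, and Protocol 8.4.1 refers to intervals in the plural. Reporting by age on the FAS is therefore within what the protocol foresaw.

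Nor would the obvious edit settle much. Defining three bands and adding the two combined rates gives five rates with none named as key. It would also leave SAP 1.3 promising at most 20 points in each age group, while the smaller younger band has a worst-case width of at least 28.9.

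**Conclusion.** The concern does not call for a change. It is a gap in detail that analysts fill sensibly: a total column in an SVR12 table by age is routine, and its counts follow from the columns already planned. Run as written, SAP 6.1.2 gives valid rates with exact intervals on the right population. No test or comparison is planned, and no decision rule uses the SVR12 rate by age, so the grouping cannot alter a conclusion. The wider intervals in the younger bands come from the number of children in them, which rewording would not change.

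This rests on three things: the bands are nested, with the same endpoint and imputation rules throughout; the study report shows counts as well as percentages; and the efficacy analysis stays descriptive, as SAP 6.1.2 says. The band sizes and response rates used above are assumptions, but the conclusion does not depend on them, because the pooled counts can be recovered under any split.
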